### **Study Duration**

18 months will be required to recruit and scan 25 cough patients and 25 age/ sex matched healthy controls, this includes 6 months for fMRI data analysis which is time consuming. Total study duration will be 18 months.

### **Statistical analysis plan**

Our team has previously published in detail our methods for analyzing functional brain imaging data with associated psychophysical metrics, many of which have been rigorously optimized by our group to control for confounding respiratory noise. We have extensive experience in these types of studies and all the required expertise to analyze and interpret brain imaging data exists within A/[name] research team in Melbourne. This includes investigating relationships between behavioral measures and brain responses (e.g., see ref 10). [name] and [name] will contribute to the interpretation of clinical metrics related to cough phenotype and cough questionnaire survey results.

### *Variables/Time Points of Interest*

Two types of data will be collected, (1) Blood Oxygen Level Dependent signal data collected during fMRI scans and used to determine regional brain activity, and (2) psychophysical data during preliminary testing sessions and during fMRI scanning. The latter includes the stimulus dose evoking 2 coughs (C2), the stimulus dose required for the initial detection of an urge to cough (Cu) and the maximal suppressive stimulus dose where a participant can resist coughing (Smax). As part of the clinical work up of the patients we will also collect

subjective patient scores of their cough severity and quality of life, using validated tools (the Leicester Cough Questionnaire (LCQ)) which can be also used to help interpret fMRI data. The primary variable of the study is the stimulus delivered (ATP versus capsaicin) compared between cough patients and healthy controls, assessing the differential outcomes on BOLD signal changes and associated psychometrics.

### *Statistical Methods*

Statistical analysis of psychophysical parameters will be performed with SPSS 22.0. Independent t- tests will be used to test the effects of group on C2, Cu and Smax thresholds. A repeated-measures ANOVA is used to test the effects of group, dose and their interaction on urge-to-cough ratings in response to random stimulus challenges. Independent t-tests will be used to assess group effects on capsaicin/ ATP doses and urge-to-cough ratings associated with the fMRI scanning.

fMRI image analysis will be performed with FEAT, version 5.98. Regressors for each dose of capsaicin/ ATP and rating events will be included in a general linear model that also includes motion parameters and confound variables to take account of physiological noise. Contrasts for capsaicin/ ATP doses will be averaged across the three scans for each participant and used in the analysis of group and between-group effects. Group contrasts include high doses for all participants (Like-Behaviour), and activation levels will be tested for correlations with Cu and frequency of coughing during repeated stimulus challenges. Higher level analyses will be carried out for inter-group averaging and between-group comparisons. Z (Gaussianised T/F) statistic images are thresholded to define clusters of contiguous voxels activated at a significance level of  $Z > 2.3$ . To correct for multiple comparisons, a corrected cluster probability threshold (based on Gaussian Random Field Theory of  $p < 0.05$ ) is applied. Between-group contrasts are made using two different comparisons: i) during the inhalation of Smax for all individuals in both groups (matched urge-to-cough sensation). Activation levels associated with Smax doses are tested for relationships with the Cu threshold and the frequency of coughing during the psychophysical sessions.

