### **Study Design**

The study will involve 25 participants with cough hypersensitivity and 25 age and sex matched healthy controls. All participants will provide written informed consent to participate in the study, which will be approved by the Melbourne Health Human Research Ethics Committee (Australia). Before inclusion, all participants undergo screening interviews to ascertain their eligibility for the study. All participants will be non-smokers with no history of neurological disease or any recent history (over 8 weeks) of acute respiratory infections. Cough hypersensitive participants will be recruited from respiratory specialist clinics and included if they have experienced chronic cough (coughing for over 8 weeks) and are considered idiopathic/ refractory coughers (to avoid the confounds of heterogeneity of precipitating diseases). Healthy control participants will have no history of chronic respiratory disease and will be individually age and sex matched to each cough hypersensitive participant.

Participants will attend two experimental sessions. The first is used to ascertain their individual sensitivities and tolerances to inhaled challenges with capsaicin and ATP

(psychophysical testing session) and the second to determine their brain responses to challenge stimuli (brain imaging session). This is not an interventional study but rather a comparison between responses in healthy control participants versus patients with chronic cough syndrome.

All participants will first undergo a psychophysical testing session where their level of sensitivity to capsaicin and ATP is measured using a method of limits approach. The following measures of sensitivity are determined: stimulus dose evoking 2 coughs (C2), the stimulus dose required for the initial detection of an urge to cough (Cu) and the maximal suppressive stimulus dose where a participant can resist coughing (Smax). Patients will provide subjective measures of their urge-to-cough using an eleven point numerical rating scale (0, no urge-to-cough; 10, maximum urge-to-cough) evoked by single breath challenges with tussive stimuli. The capsaicin and ATP solutions are nebulized to participants via a

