facemask fabricated to deliver stimuli through oral breathing (and to be compatible for hands free use in an MRI scanner). Doubling doses of stimuli are used throughout the study ranging from 0.06 $\mu$ M to 125 $\mu$ M for capsaicin and 0.45 – 232.5mM for ATP. Once the C2 dose is identified, participants will receive randomized challenges with doses two increments above and below the C2 (C2-2, C2-1, C2, C2+1 and C2+2) to accurately measure the stimulus response function for each individual. Finally, in preparation for fMRI scanning, participants will be challenged for 24 seconds with stimuli above and below the C2 dose to determine challenge stimuli doses that are tolerable for brain imaging (defined as the Smax). This session is used to ascertain each participant's sensitivities and tolerances to inhaled stimuli and to inform the participants about the design of the subsequent fMRI session.

In the second session, participants return for fMRI scanning. Structural and functional MRI data are collected on a Siemens Magnetom Trio 3 Tesla scanner (Siemens AG, Erlangen, Germany) with a 32-channel head coil located at the Monash Biomedical Imaging Facility, Melbourne, Australia. Anatomical T1 - weighted images are acquired in the sagittal plane (192 slices, 0.90 mm slice thickness, 0.84  $\times$  0.84 mm^2 in - plane resolution, echo time (TE) = 2.59 ms, repetition time (TR) = 1900 ms, flip angle = 9). Two functional MRI (fMRI) scans of 491.4 seconds duration are performed using the BOLD contrast. Functional runs are collected using a partial field of view (FOV) with a gradient-echo echo-planar parallel imaging sequence (GRAPPA, PAT factor=3, reference lines=36, TR=1790ms, TE=30ms, 27 slices, 2.5mm thickness, 1.88mm in-plane resolution, flip angle=70 degrees). This facilitates a restricted focus on the brainstem necessary to define regional activations in this area (see Figure 2).

During image acquisition, participants lay comfortably on the scanner bed with their head stabilised with foam padding and hearing protection. Participants are fitted with the facemask and apparatus used in the psychophysical testing session. Online respiratory monitors are fitted around their chest throughout the experiment (AD Instruments). A periscope mirror attached to the scanner head coil enables participants to view a projector

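### Controls are individually matched on age and sex, but the named psychophysical group tests ignore both, so intervals may be wider than needed

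*Combined protocol and SAP*

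**What the plan says.** Study Design plans 25 patients and 25 healthy controls, and each control "will be individually age and sex matched to each cough hypersensitive participant".

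Statistical Methods gives the psychophysical tests:

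- Thresholds: "Independent t- tests will be used to test the effects of group on C2, Cu and Smax thresholds".
- Scanner session: "Independent t-tests will be used to assess group effects on capsaicin/ ATP doses and urge-to-cough ratings associated with the fMRI scanning".
- Ratings in the randomised challenges: "A repeated-measures ANOVA is used to test the effects of group, dose and their interaction on urge-to-cough ratings".

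For the imaging data, the nuisance terms named are for head motion and physiological noise. The group level is described only by "Higher level analyses will be carried out for inter-group averaging and between-group comparisons", without a list of terms. Age, sex and pair appear in none of these analyses.

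On dosing, Study Design says "Doubling doses of stimuli are used throughout the study", with a top of "232.5mM for ATP". It then continues: "Once the C2 dose is identified, participants will receive randomized challenges with doses two increments above and below the C2". Neither section says whether thresholds are analysed as concentration or as doubling step, or what value is entered for someone who does not reach C2.

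**The concern.** Individual matching makes the two members of a pair alike to the extent that age and sex drive the outcome. An independent t-test leaves that shared variation in the error term. Its standard error is then too large, its true type I error falls below the nominal level, and some of the benefit of matching is lost. With 25 per group, a cheap gain in precision is worth taking.

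Two further details are secondary and conditional.

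- **Ceiling.** Preliminary Data describes ATP as a weak cough stimulus in healthy people and reports that patients are more sensitive to it. If some participants have no ATP C2, most would probably be controls, and leaving them out would shrink the ATP group difference.
- **Rating ANOVA.** It uses five levels around each person's own C2. Someone whose C2 lies in the first two or last two steps of the ladder lacks at least one level, and a complete-case analysis would drop that person.

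**Working it through.** **The plan's own figure.** Power/Sample Size claims at least 80% power for 0.48 to 0.72 SD in BOLD regions of interest. A two-sided 5% two-sample t-test with 25 per group gives 38% at 0.48 SD and 70% at 0.72 SD (one-sided: 51% and 81%). The plan used fMRIpower with inputs that are not shown, so this mismatch is a separate matter. Below, 0.72 SD is only a reference size.

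**Inputs.** 25 per group and individual matching come from Study Design. Assumed: two-sided alpha 0.05 (not stated for the t-tests), exact matching, and a share R² of within-group variance explained by age and sex. Under exact matching R² equals the within-pair correlation.

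**Half-widths, in SD units**

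- Independent t-test: t(48) × √(2/25) = 2.011 × 0.2828 = 0.569.
- Group plus age and sex: t(46) × √(2(1 − R²)/25) = 2.013 × 0.2828 × √(1 − R²).
- Paired t-test: t(24) × √(2(1 − ρ)/25), with t(24) = 2.064 and ρ the pair correlation.

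| R² (assumed) | Half-width, independent | Half-width, covariates | Type I error, independent | Power at 0.72 SD, independent | Power at 0.72 SD, covariates |
|---|---|---|---|---|---|
| 0% | 0.57 | 0.57 | 5% | 70% | 70% |
| 10% | 0.57 | 0.54 | 3.9% | 71% | 75% |
| 20% | 0.57 | 0.51 | 2.9% | 72% | 80% |
| 30% | 0.57 | 0.48 | 2.0% | 74% | 85% |

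The type I errors and the independent-test powers come from simulation under matching.

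**Break-even.** Covariates gain once R² exceeds 1 − (t(48)/t(46))² = 0.2%. A paired test gains only once ρ exceeds 1 − (t(48)/t(24))² = 5.1%. At ρ = 0 its half-width is 0.584, or 2.6% wider than the independent test. It also discards anyone whose partner is lost.

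**ATP ceiling (secondary).** log2(232.5/0.45) = 9.01, so the ladder has 10 steps. Assumed: normal log2 thresholds with SD 2 doublings and a true difference of 0.72 × 2 = 1.44 doublings. The table gives the simulated estimate in doublings, with power in brackets.

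| Controls without C2 (assumed) | Dropped | Scored at top dose |
|---|---|---|
| 7% | 1.23 (61%) | 1.36 (69%) |
| 16% | 1.04 (50%) | 1.24 (68%) |
| 31% | 0.84 (37%) | 1.05 (65%) |

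A rank test that ranks these participants highest has power 67/67/66%. A right-censored model with age and sex, where these explain nothing, estimates 1.43 at both 7% and 31%, with power 68% and 67%. Its type I error is 5.0–5.4% with an F reference and 6.2–6.5% with chi-square. Raw dose scored at the top gives power 56/61/62%. With under 1% at the ceiling it gives 43%, against 70% on log2.

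**Rating ANOVA (secondary).** Under the same spread, the share of people with a C2 who lack at least one of the five levels is 13% of controls against 23% of patients at a control mean step of 5. At a mean step of 9 it is 55% against 34%. The direction is not stable, and no resulting bias was computed.

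**The case against.** The strongest reply is that an unadjusted test after matching is valid and errs on the safe side. The gain from adjustment depends on a number that the documents do not give, and at 10% or less it is small. This stands, so the point is worded as a possible loss of precision.

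A reader might infer more in three places, and the documents do not support it.

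- **That ignoring the matching biases the comparison or produces false positives.** With positive pair correlation the error rate falls.
- **That age and sex are left out of the fMRI group model.** Statistical Methods does not list the group-level terms, and the opening of the Statistical analysis plan points to published methods not available here. The terms are unstated, not shown to be absent. The figures above are for a single-outcome t-test and do not carry over directly to cluster-corrected voxelwise inference.
- **That participants without an ATP C2 will be numerous, or will be dropped.** Preliminary Data says healthy participants coughed less to ATP than to capsaicin, not that they failed to reach two coughs. No handling is stated. With top-coding or a rank test little power is lost, although top-coding still shrinks the estimate. The disadvantage of raw dose also narrows, to about 3 points against top-coded log dose at a 31% ceiling.

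Complete-case handling of the rating ANOVA is likewise an assumption. What survives the reply is that covariates lose essentially nothing when age and sex explain nothing, and that scale and non-reacher rules are missing detail that is easily supplied.

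**Conclusion.** The concern holds in this limited form. Matching on age and sex is not used in the named psychophysical tests. Those tests are valid but conservative if age and sex matter. The half-width could fall from 0.57 SD to between 0.54 and 0.48 SD if age and sex explain 10 to 30% of variance, and would not change at 0%. That share is an assumption throughout, as are exact matching and two-sided 5% testing.

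The scale, ceiling and missing-level points are secondary. They matter materially only under handling that the plan neither adopts nor rules out: dropping participants, or analysing raw dose when few are at the ceiling. Their size rests on an assumed spread, shift and ceiling rate. Adding the covariates is a nearly free improvement.

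**What to change.** 1. Replace the independent t-tests on C2, Cu, Smax, scanner doses and scanner ratings with linear models of group plus age and sex. List age and sex in the group-level fMRI model too.
2. State that thresholds are analysed as log2 dose (doubling step).
3. Keep a participant with no ATP C2 at the top dose in the C2 analysis, as right-censored (with an F or t reference) or ranked highest. Do the same for Smax only where the participant still resists coughing at the top dose. Study Design sets Smax from challenges around C2, so also say how Smax is recorded when there is no C2. Do not apply the rule to Cu, for which no ceiling is shown. Report ceiling counts by group and stimulus.
4. If a mixed model replaces the rating ANOVA so that people lacking some levels are kept, fit it per stimulus, or include group-by-stimulus and group-by-dose terms. Otherwise the ATP versus capsaicin comparison named under Variables/Time Points of Interest is pooled away. Report how many people have no C2, because these challenges start only once C2 is found and no model can recover their ratings.

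The cost is SAP wording, 2 degrees of freedom and modest analysis work. Age and sex are already needed for matching. Censored regression may need software other than SPSS 22.0. No dose or study procedure changes.

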screen upon which visual instructional cues are presented throughout the experimental session. Within each functional scanning run, three stimulus blocks of capsaicin, three of ATP and two of saline are administered in a pseudorandom order. Each stimulus block lasts 24 seconds in duration, and is separated from the next by 36.8 seconds. Visual cues are used to time the participant's inhalation with the onset of stimulus delivery in order to standardise the respiratory cycle between participants. At the end of each challenge block, participants give a numerical rating of their urge-to-cough.

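### The ATP-versus-capsaicin comparison between patients and controls is set as primary and includes the psychometrics, but no psychophysical test has a stimulus term

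*Combined protocol and SAP*

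**What the plan says.** The Variables/Time Points of Interest section states: "The primary variable of the study is the stimulus delivered (ATP versus capsaicin) compared between cough patients and healthy controls", with the purpose of "assessing the differential outcomes on BOLD signal changes and associated psychometrics". The psychometrics are thus inside the primary comparison.

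Stimulus varies within participant. In the first session, for every participant, "their level of sensitivity to capsaicin and ATP is measured using a method of limits approach" (Study Design). In each scanning run, "three stimulus blocks of capsaicin, three of ATP and two of saline are administered in a pseudorandom order". Every participant can therefore supply an ATP value and a capsaicin value.

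Statistical Methods then lists three psychophysical analyses:
- For thresholds: "Independent t- tests will be used to test the effects of group on C2, Cu and Smax thresholds".
- For ratings during the randomised challenges: "A repeated-measures ANOVA is used to test the effects of group, dose and their interaction on urge-to-cough ratings".
- For the doses and ratings at the scan: independent t-tests of group.

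None includes stimulus as a factor. The plan does not say whether these tests are run once per stimulus or on pooled data, although its mention of capsaicin/ATP doses suggests the former. It gives no rule for interpreting different results for the two stimuli, and the Multiplicity section is marked not applicable.

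**The concern.** The stated comparison asks whether the patient-control difference is larger for one stimulus than for the other. A group test within ATP and a second one within capsaicin do not answer that, because the contrast between significant and non-significant is not itself a test. Pooling the stimuli does not answer it either, since it averages away the quantity of interest.

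The distinction matters in this population. The Background describes hypersensitivity as a key common feature of chronic cough, so a lower ATP threshold in patients is compatible with general sensitisation. Capsaicin is the natural comparator: the Preliminary Data section expects it to activate both vagal pathways, and ATP only one. Without the direct contrast, the behavioural data can neither support nor oppose a selective change for ATP.

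**Working it through.** **Question set against tests**

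| Measure | Planned terms | Tests group-by-stimulus? |
|---|---|---|
| C2, Cu, Smax | group | no |
| Ratings, randomised challenges | group, dose, group-by-dose | no |
| Scan doses, scan ratings | group | no |

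**The plan's own figure.** No power is stated for thresholds, ratings or a group-by-stimulus effect. The only power statement (at least 80% for 0.48 to 0.72 SD) concerns BOLD regions of interest and rests on data in a figure not shown. A plain two-sided independent t-test with 25 per group gives 38% at 0.48 SD and 70% at 0.72 SD, so the statement is not reproduced this way. Nothing below depends on it.

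**Inputs.** From Study Design: "25 participants with cough hypersensitivity and 25 age and sex matched healthy controls", both stimuli per participant. Assumed, because the documents give no values: two-sided 0.05; correlation rho of 0.3 to 0.7 between a person's two thresholds; equal SDs of the two log2 thresholds; no unreached thresholds; the same true standardised group shift d for both stimuli.

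**How often separate tests would split.** Simulation, 40,000 studies per scenario, with no true stimulus-specific effect:

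| d | Power per stimulus | ATP only significant | Exactly one significant |
|---|---|---|---|
| 0.57 | 51% | 13-20% | 26-40% |
| 0.8 | 79% | 9-14% | 18-28% |
| 1.0 | 93% | 4-6% | 8-11% |
| 1.2 | 99% | about 1% | 2-3% |

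The higher figure in each range belongs to rho = 0.3. Under these assumptions the direct group-by-stimulus test rejects in 5%.

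**Precision of the direct test.** For D = log2(ATP threshold) - log2(capsaicin threshold), SD(D) = SD x sqrt(2(1 - rho)). The standard error relative to a single-stimulus test is therefore sqrt(1.4) = 1.18 at rho 0.3, 1.00 at 0.5 and sqrt(0.6) = 0.77 at 0.7. With 25 per group, 80% power needs 0.809 SD for a single stimulus. For the interaction, in single-stimulus SD units:
- rho 0.3: 0.809 x 1.183 = 0.96
- rho 0.5: 0.809 x 1.000 = 0.81
- rho 0.7: 0.809 x 0.775 = 0.63

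**How far the 5% depends on its assumptions**
- Unequal SDs. If one stimulus has 1.5 or 2 times the log2-threshold SD of the other, equal standardised shifts of 0.57 to 0.8 SD are unequal in doubling doses. The test then rejects in 10-26% (ratio 1.5) or 17-46% (ratio 2). Such a rejection reflects a true difference in doubling doses, but not a difference in standardised shift.
- Capping. The dose ranges span log2(125/0.06) = 11.0 doublings for capsaicin and log2(232.5/0.45) = 9.0 for ATP, and the Preliminary Data section reports that healthy participants coughed less to ATP than to capsaicin. If half of the controls' ATP thresholds lay above the range (an assumption) and were set to the ceiling, the test would reject in 15-33% at 0.8 to 1.2 SD with no true interaction.

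**The case against.** A reader might infer that the investigators intend to read a result significant for ATP but not for capsaicin as ATP-specific hypersensitivity. The documents do not support that: no such rule is stated, and the tests are not explicitly run by stimulus. The misreading is a risk that the plan leaves open, not an announced step.

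A reader might also infer that the central hypothesis stands or falls on this contrast. It does not. The objective concerns ATP-sensitive pathways in the brainstem and brain, and the hypotheses concern ATP acting through jugular pathways, to be judged mainly by where activation occurs. Neither requires a larger threshold shift for ATP than for capsaicin. The first session also serves to establish tolerances and choose scanning doses. This limits the importance of the gap but does not close it, because the plan itself puts the psychometrics inside the primary comparison.

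The split rates depend on the assumed effect. Power near 50% is close to where splits are commonest, and with large shifts they almost vanish. The direct test has limits too: modest power, and sensitivity to unequal SDs and to unreached thresholds. All of this stands and is carried into the conclusion and the fix.

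**Conclusion.** The omission is clear from the text: a group-by-stimulus comparison that includes the psychometrics is set, and none of the listed psychophysical analyses estimates it. This holds whether the tests are run by stimulus or pooled.

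The size of the consequence is illustrative only. With equal standardised shifts, an ATP-only result ranges from about one study in five to about one in a hundred, depending on a shift and a correlation that the documents do not give. The 5% error rate and the standard-error ratio of 0.77-1.18 hold for equal log2-threshold SDs and no capping. A non-significant interaction would not show equal sensitisation, since only interactions of about 0.63-0.96 SD are detectable with 80% power. The point does not invalidate the data and makes no claim about the imaging analysis.

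**What to change.** Amend Statistical Methods as follows.

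1. For C2, Cu and Smax, compute log2(ATP threshold) minus log2(capsaicin threshold) per participant and compare it between groups. Report the difference in doubling doses with a 95% interval. The log2 scale suits the design ("Doubling doses of stimuli are used throughout the study") and removes the difference in units. The same contrast can be applied to scan doses, and the raw ATP-minus-capsaicin difference to scan ratings.
2. Add stimulus to the ratings ANOVA, with group-by-stimulus and group-by-stimulus-by-dose terms. State whether dose is coded as steps from C2 or as concentration; steps are comparable across stimuli, concentrations are not.
3. Treat thresholds not reached within the tested range as censored, for example by interval-censored or Tobit-type regression, rather than capping or dropping them. Report their number by group and stimulus.
4. State that any claim of behavioural ATP-specificity rests on this contrast, that its interval will be reported whatever the p-value, and that a non-significant result is not evidence of equal sensitisation.

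The cost is SAP wording and a somewhat more complex threshold model. No new participants, procedures or measurements are needed. The price is modest power, which should be stated in advance with the detectable sizes above.

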We have generated functional brain imaging (fMRI) data to suggest that the different brain circuits in receipt of nodose and jugular ganglia neuron inputs (as identified in animal studies) are conserved in humans. When inhaled, the tussigenic compound capsaicin (from hot chili peppers) indiscriminately stimulates both nodose and jugular chemosensitive afferents and we have published that capsaicin inhalation produces brain activations in the primary sensory, anterior and mid-insula, cingulate, premotor, motor and orbitofrontal cortices (29, 30). These regions are presumed to encode perceptual awareness of airway irritation, and the associated emotional, cognitive and behavioral (motor) consequences. For example, activity in the human primary sensory cortex (which receives jugular ganglia inputs in animal studies) correlates with an individual's perception of airway irritation (their perceived need/ urge to cough) while activity in the insula (in receipt of nodose inputs) relates closely to the actual magnitude of the delivered stimulus independent of perception. We have now built upon these published findings by using high resolution brainstem fMRI during the inhalation of ATP (expected to only activate P2X2/3 expressing nodose-derived airway afferents) versus capsaicin (expected to activate both jugular and nodose chemosensitive afferents). Our results are striking and reveal that ATP inhalation evokes an increased signal level in the brainstem regions corresponding to the nTS, while capsaicin inhalation produces activations in both the nTS and in an area of the dorsal spinal trigeminal nucleus on the lateral margins of the brainstem that contains the paratrigeminal nucleus (Fig 2). Indeed, our healthy participants did not cough as much to ATP compared to capsaicin, consistent with studies of cough in animals and humans and the relatively poor cough-evoking properties of ATP in healthy humans (20, 21). However, the perception of airway irritation was identical between ATP and capsaicin stimuli (Fig 3). We believe that cough production will ultimately be dependent upon activation of the neural circuit that integrates in the paratrigeminal nucleus (i.e. the jugular afferent pathway) and therefore

***we hypothesize that there is an upregulation of the capacity of ATP to act via jugular ganglia pathways in chronic cough patients.***

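### The activation-behaviour correlations name no group term and do not say whether they are pooled; if pooled, a patient-control difference cannot be told apart from an individual-level relationship

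*Combined protocol and SAP*

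**What the plan says.** The study compares two groups: "The study will involve 25 participants with cough hypersensitivity and 25 age and sex matched healthy controls" (Study Design).

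Statistical Methods, in the statistical analysis plan, sets up the activation-behaviour analyses twice:

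- The first statement shares a sentence with a contrast over everyone: "Group contrasts include high doses for all participants (Like-Behaviour"; the sentence then continues that "activation levels will be tested for correlations with Cu and frequency of coughing during repeated stimulus challenges".
- The second comes directly after a between-group contrast made "during the inhalation of Smax for all individuals in both groups (matched urge-to-cough sensation". It reads: "Activation levels associated with Smax doses are tested for relationships with the Cu threshold and the frequency of coughing during the psychophysical sessions".

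Neither statement names a group covariate, a group-by-measure interaction or a restriction to one group. The only adjustment variables named are scan-level, in a "general linear model that also includes motion parameters and confound variables to take account of physiological noise". The same section does name group for the t-tests on C2, Cu and Smax, and for the repeated-measures ANOVA of urge-to-cough ratings.

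**The concern.** A correlation computed across two groups mixes two sources of information: how the measures move together within each group, and how the group means differ. If the means of both variables differ, the pooled correlation is non-zero even when the variables are unrelated within each group.

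The plan expects both means to differ. Preliminary Data cites patients as more sensitive than non-cough subjects to inhaled ATP, and the plan tests Cu for a group effect. The hypothesis is that ATP-sensitive activation is altered in chronic cough, and Power/Sample Size plans for a group difference in activation.

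If patients have lower Cu and greater activation, the artefact is a negative Cu-activation correlation. A reader would take that as activation tracking individual sensitivity. The study could then report its group comparison a second time as if it were separate mechanistic evidence. Because the plan leaves the population open, the choice between pooled and within-group analysis could also be made after the data are seen.

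**Working it through.** **Inputs**

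- Group sizes: 25 patients and 25 controls (Study Design).
- Group difference in activation, dB: 0.48 to 0.72 SD (Power/Sample Size). This is a detectable difference, not a forecast of the observed one.
- Group difference in Cu, dC: the documents give no means or SDs. Assumed 0.5 to 2.0 within-group SD.
- Within-group correlation: zero, the null case.
- Test: one region of interest, two-sided 5%. The plan gives neither sidedness nor a region-level alpha for these tests, so this is an assumption.
- Both measures taken as normal within group.

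**The plan's own figure.** The plan gives no figure for the correlations. The nearest is at least 80% power for 0.48 to 0.72 SD. With 25 per group, power ≈ Φ(d√(n/2) − z):

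- d = 0.48: 0.48 × √12.5 = 1.697, giving 39.6% two-sided and 52.1% one-sided.
- d = 0.72: 0.72 × √12.5 = 2.546, giving 72.1% two-sided and 81.6% one-sided.

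Only d = 0.72 one-sided reaches 80%. The inputs to the plan's power software are not given, and this mismatch is a separate matter. Here 0.48 and 0.72 serve only as effect sizes, and the result below does not depend on the power claim.

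**Step 1: pooled correlation produced by group means alone.** With equal groups and zero within-group correlation,

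|r| = (dB·dC/4) / √[(1 + dB²/4)(1 + dC²/4)]

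- dB = 0.48, dC = 0.5: 0.06 / √(1.0576 × 1.0625) = 0.057
- dB = 0.72, dC = 1.0: 0.18 / √(1.1296 × 1.25) = 0.151
- dB = 0.72, dC = 2.0: 0.36 / √(1.1296 × 2) = 0.240

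**Step 2: false rejection.** Simulating 40,000 studies per setting gives the following rates. The pooled test is Pearson on 48 df; the adjusted test is the partial correlation given group, on 47 df.

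| dB | dC | Pooled | With group term |
|---|---|---|---|
| 0.48 | 0.5 | 6.7% | 5.1% |
| 0.48 | 1.0 | 11.2% | 5.1% |
| 0.48 | 1.5 | 16.4% | 5.0% |
| 0.48 | 2.0 | 21.3% | 5.0% |
| 0.72 | 0.5 | 9.0% | 5.1% |
| 0.72 | 1.0 | 18.7% | 4.8% |
| 0.72 | 1.5 | 30.3% | 5.0% |
| 0.72 | 2.0 | 40.7% | 5.3% |

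When dB or dC is zero, the pooled test stays at 4.8% to 5.2%.

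**Step 3: check without simulation.** Fisher's z has standard error 1/√47.

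- dB = 0.72, dC = 1.0: atanh(0.151) × √47 ≈ 1.05. Φ(1.05 − 1.96) plus the small opposite tail is about 18%.
- dB = 0.72, dC = 2.0: atanh(0.240) × √47 ≈ 1.67, giving about 39%.

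Both are close to the simulated values.

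**The case against.** **Pooling is not written.** A reader might infer that the plan specifies correlations over all participants. It does not. In the first statement, the reference to all participants describes the high-dose contrast. In the second, the reference to both groups describes a between-group contrast. The section also lists group and between-group effects separately, so a group contrast may mean a within-group average. The opening of the statistical analysis plan points to the team's earlier published work on brain-behaviour relationships, which is not available here and supports neither reading. This objection stands: the defect is an unstated population and a missing group term, not a specified pooled analysis.

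**A pooled correlation is not only the group comparison.** A true within-group slope would also produce one. The supportable claim is that the two cannot be distinguished.

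**A Cu difference is expected, not guaranteed by selection.** Patients are described as hypersensitive, but the listed entry criteria are duration of cough and idiopathic or refractory status. No Cu threshold is applied.

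**The size is conditional.** The top rate needs a Cu difference of 2.0 SD together with the larger activation difference. The Smax contrast is intended to match urge-to-cough; if activation does not differ between groups there, nothing is inflated. The rates are for one regional test and do not carry over to the planned cluster-corrected search at Z > 2.3.

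**Dose as a second explanation.** Each person is scanned at an individual Smax, so a reader might infer that a Cu correlation is really a dose effect. The support in Preliminary Data is that insula activity "relates closely to the actual magnitude of the delivered stimulus independent of perception". The functional scans, however, use a partial field of view focused on the brainstem, and the documents do not say that brainstem signal follows dose or that Smax falls with Cu. Adjusting for Smax could also remove real signal if it does track Cu. This is too weak to require a change.

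**The main comparison does not rest on these tests.** Variables/Time Points of Interest makes the primary comparison ATP versus capsaicin between groups. The correlations support its interpretation, and nothing here undermines the primary analysis.

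**Conclusion.** The concern holds in conditional form. The plan names no group term for these correlations and does not say whether they are pooled, although it names group for its other psychophysical tests. If they are pooled, as the text most naturally reads, a patient-control difference in both variables can pass for an individual-level relationship.

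For one regional test at two-sided 5% with no within-group relationship, false rejection is about 7% to 41%, against about 5% with a group term. This rests on the plan's detectable activation difference of 0.48 to 0.72 SD, taken as real, and on an assumed Cu difference of 0.5 to 2.0 SD. The rate stays near 5% if either difference is absent. The upper end should not be quoted without those conditions.

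The correction is worth making because it removes the ambiguity at little cost. It concerns supporting analyses and does not challenge the between-group contrasts.

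**What to change.** Replace both correlation statements with one specification, along these lines:

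> Activation will be regressed on Cu and, in a separate model, on cough frequency, with group (patient or control) as a covariate. The slope within each group will be reported with its confidence interval. Any conclusion that activation relates to individual sensitivity will rest on the group-adjusted (within-group) slope.

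A group-by-measure interaction may be reported as exploratory. A further model adjusting for Smax dose is optional and not part of the required change.

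**Cost.** This is a wording change and needs no new data. The group term takes one degree of freedom (48 to 47). Some power is lost if the true relationship lies mainly between groups. Slopes in each group will be imprecise: with 25 people, a 95% interval around a correlation of zero is about ±tanh(1.96/√22) = ±0.40. The separate slopes are therefore descriptive, and the group-adjusted slope from all 50 participants should carry the inference.
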